5.3 General Concomitant Medication and Supportive Care Guidelines

Medications or vaccinations specifically prohibited in the exclusion criteria are not allowed during the ongoing trial. If there is a clinical indication for one of these or other medications or vaccinations specifically prohibited during the trial, discontinuation from trial therapy or vaccination may be required. The investigator should discuss any questions regarding this with CTEP. The final decision on any supportive therapy or vaccination rests with the investigator and/or the subject's primary physician; however, the decision to continue the subject on trial therapy or vaccination schedule requires the mutual agreement of the Investigator, CTEP, and the patient.

Acceptable Concomitant Medications

All treatments that the investigator considers necessary for a patient's welfare may be administered at the discretion of the investigator in keeping with the community standards of medical care. All concomitant medication will be recorded on the case report form (CRF) including all prescription, over-the-counter (OTC), herbal supplements, and IV medications and

fluids. If changes occur during the trial period, documentation of drug dosage, frequency, route, and date may also be included on the CRF.

All concomitant medications received within 28 days before the first dose of trial treatment and 30 days after the last dose of trial treatment should be recorded. Concomitant medications administered after 30 days after the last dose of trial treatment should be recorded for SAEs.

Prohibited Concomitant Medications

Patients are prohibited from receiving the following therapies during the Screening and Treatment Phase (including retreatment for post-complete response relapse) of this trial:

- Anti-cancer systemic chemotherapy or biological therapy or any other investigational cancer therapy other than those being investigated in this study.
- Immunotherapy not specified in this protocol.
- Live vaccines within 30 days prior to the first dose of trial treatment and while participating in the trial until 30 days after last dose of study drug. Examples of live vaccines include, but are not limited to, the following: measles, mumps, rubella, chicken pox, yellow fever, rabies, BCG, and typhoid (oral) vaccine. Seasonal influenza vaccines for injection are generally killed virus vaccines and are allowed; however, intranasal influenza vaccines (e.g. Flu-Mist®) are live attenuated vaccines, and are not allowed.
- Glucocorticoids for any purpose other than to modulate symptoms from an event of suspected immunologic etiology. The use of physiologic doses of corticosteroids may be approved after consultation with the Sponsor.
- Additional radiation therapy non-specified in the protocol.
 - o Note: If the patient develops indication for urgent palliative radiation such as brain metastases or spinal cord compression (either within the previously irradiated field or outside), the patient will be considered to have progressed (see below) and will be removed from the trial.
- Drugs with laxative properties and herbal or natural remedies for constipation should be used with caution through to 90 days after the last dose of tremelimumab during the study
- Sunitinib should not be given concomitantly or through 90 days after the last dose of tremelimumab (acute renal failure has been reported with combination therapy of tremelimumab and sunitinib)
- EGFR tyrosine kinase inhibitors should not be given concomitantly, and should be used with caution in the 90 days post last dose of durvalumab. Increased incidences of pneumonitis (with third generation EGFR TKIs) and increased incidence of transaminase increases (with 1st generation EGFR TKIs) has been reported when durvalumab has been given concomitantly.
- Herbal and natural remedies which may have immune-modulating effects should not be given concomitantly unless agreed by the sponsor

Patients who, in the assessment by the investigator, require the use of any of the aforementioned treatments for clinical management should be removed from the trial. Patients may receive other medications that the investigator deems to be medically necessary.

The Exclusion Criteria describe other medications that are prohibited in this trial. There are no prohibited therapies during the Post-Treatment Follow-up Phase.

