- 3.2.16 Active or prior documented autoimmune or inflammatory disorders (including inflammatory bowel disease, diverticulitis (with the exception of diverticulosis), sarcoidosis syndrome, or other serious GI chronic conditions associated with diarrhea; systemic lupus erythematosus; Wegener syndrome[granulomatosis with polyangiitis]; Graves' disease; rheumatoid arthritis; hypophysitis; uveitis; sarcoidosis syndrome, etc.) within the past 3 years prior to the start of treatment. The following are exceptions to this criterion:
- Patients with vitiligo or alopecia
 - Patients with hypothyroidism (eg, following Hashimoto syndrome) stable on hormone replacement or psoriasis not requiring systemic treatment
 - Any chronic skin condition that does not require systemic therapy
 - Patients without active disease in the last 5 years may be included but only after consultation with the study physician
 - Patients with celiac disease controlled by diet alone
- 3.2.17 History of another primary malignancy except for
- Malignancy treated with curative intent and with no known active disease ≥ 5 years before the first dose of study drug and of low potential risk for recurrence ^[1-3]_[SEP]
 - Adequately treated non-melanoma skin cancer or lentigo maligna without evidence of disease
 - Adequately treated carcinoma in situ without evidence of disease (eg, cervical cancer in situ)

- 3.2.18 Mean QT interval corrected for heart rate (QTc) ≥ 470 ms calculated from electrocardiograms (ECGs) using Fridericia's Correction. Abnormal ECGs should be repeated.
- 3.2.19 History of active primary immunodeficiency
- 3.2.20 Known history of previous clinical diagnosis of tuberculosis
- 3.2.21 Active infection including hepatitis B (known positive HBV surface antigen (HBsAg) result or, hepatitis C. Patients with a past or resolved HBV infection (defined as the presence of hepatitis B core antibody [anti-HBc] and absence of HBsAg) are eligible. Patients positive for hepatitis C (HCV) antibody are eligible only if polymerase chain reaction is negative for HCV RNA. Negative serologies documented over the past year are sufficient evidence of this.
- 3.2.22 Receipt of live, attenuated vaccine within 30 days prior to the first dose of investigational treatment. Note: Patients, if enrolled, should not receive live vaccine during the study and up to 30 days after the last dose of investigational treatment.

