5.6 Criteria for Removal from Study

When study treatment is terminated per the criteria in Section 5.4 patients will remain on study follow-up. Study follow-up will be terminated at death or for at least one year from the time of treatment initiation and at least 12 weeks after removal from study treatment, whichever occurs first. Patients removed from study treatment for unacceptable adverse event(s) will continue on study follow-up until the preceding criteria are met or disease progression, whichever occurs later. The reason for study removal and the date the patient was removed must be documented in the Case Report Form.

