--	---

The following visits and assessments are required after discontinuing study treatment:

Days following discontinuation:

30, 60 and 90 days (+/-5 days): physical exam, vital signs, body weight, CBC with diff, serum chemistries^a, pregnancy test for WOCB (urine or serum) AE/SAE assessments, concurrent medications, and performance status

Cohort 2 – Colorectal cancer

	Pre- Study	Wk 1	Wk 2	Wk 3	Wk 4	Wk 5	Wk 6	Wk 7	Wk 8	Wk 9	Wk 10	Wk 11	Wk 12	Wk 13- 52	Off Treatment ^e
MEDI4736(durvalumab)		A				A				A				A	
Tremelimumab		B				B				B				B	
Radiation therapy			C				C				C			C	
Informed consent	X														
Demographics	X														
AE/SAE Assessments ^l	X	X				X				X				X ^e	X
Medical history	X	X				X				X				X ^e	
Concurrent meds ^d	X													X	
Physical exam	X	X				X				X				X ^e	X
Vital signs ^p	X	X				X				X				X ^e	X

Performance status	X	X				X				X				X ^e	X
CBC w/diff, plts	X	X ^b				X				X				X ^e	X
Serum chemistry ^a	X	X ^b				X				X				X ^e	X
EKG ^f	X														
Hepatitis B and C and HIV ^m	X														
Urinalysis	X ^f														
Tumor measurements	X		Tumor measurements should be performed during week 7-8 and then repeated every 12 weeks +/- 5 days. Documentation (radiologic) must be provided for patients removed from study for progressive disease.												
Radiologic evaluation ^k	X		Radiologic measurements should be performed during week 7 or 8 and then every 12 weeks +/- 5 days while on treatment.												X ^e
B-HCG	X ^b	X				X				X				X ^e	X ^e
Research blood samples	X					X									
Biopsy of site(s) of disease	X ⁱ								X ^j						
PRO-CTCAE ⁿ	X		X		X		X		X				X	X	X

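### Section 5.3 ends by saying nothing is prohibited in follow-up, which contradicts its own post-dose bars on sunitinib and live vaccines

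*Combined protocol and SAP*

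**What the plan says.** Section 5.3 lists prohibited concomitant medications. Its lead-in applies the list to the screening and treatment phase, including retreatment after relapse from a complete response. Two bullets run longer than that by their own terms:

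- **Sunitinib:** "Sunitinib should not be given concomitantly or through 90 days after the last dose of tremelimumab". The bullet gives reported acute renal failure with the combination as the reason.
- **Live vaccines:** barred for 30 days before the first dose and "while participating in the trial until 30 days after last dose of study drug".

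The section then ends: "There are no prohibited therapies during the Post-Treatment Follow-up Phase".

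The vaccine bar has a second source. Exclusion criterion 3.2.22 says that enrolled patients "should not receive live vaccine during the study and up to 30 days after the last dose of investigational treatment". Section 5.3 also refers readers to the exclusion criteria twice: "Medications or vaccinations specifically prohibited in the exclusion criteria are not allowed during the ongoing trial", and, just before the closing sentence, "The Exclusion Criteria describe other medications that are prohibited in this trial". No exclusion criterion mentions sunitinib.

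The start of the follow-up phase is not defined. Section 5.6 says "When study treatment is terminated per the criteria in Section 5.4 patients will remain on study follow-up". Section 5.5 requires at least 12 weeks of follow-up after removal from treatment, or until death. Section 10 sets the visits after discontinuation at "30, 60 and 90 days (+/-5 days): physical exam, vital signs, body weight", with laboratory tests and adverse-event checks.

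**The concern.** The bullets say that two bars continue after dosing. The lead-in and the closing sentence say that the list ends with treatment. All of these are on the face of one section, and nothing states which governs.

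What is at stake is a safety instruction. A site that relies on the closing sentence could give a live vaccine or sunitinib inside a window that the same section bars. The sunitinib case matters more, because the bar has a stated organ-toxicity reason and no second statement elsewhere to catch the error.

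**Working it through.** The plan gives no figure to reproduce. The check compares the texts and then counts how many days of each bar could fall in follow-up.

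**Inputs**

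- Dosing (5.1.1 and Section 10): both drugs every 28 days, at most 4 tremelimumab and 13 durvalumab doses.
- Sunitinib bar: 90 days after the last tremelimumab dose (5.3).
- Live-vaccine bar: 30 days after the last study drug (5.3 and 3.2.22).
- Longest permitted treatment delay: 12 weeks (5.7).

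**Assumptions**

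- Cycles run without delay.
- Because the phase start is undefined, three starts are tried: the day of the last dose (offset 0), 28 days later when the next cycle would be due, and 30 days later at the first off-treatment visit.

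**Dose days.** Dose k falls on day 1 + 28(k − 1). Dose 4 is day 85, dose 5 day 113, dose 6 day 141, dose 7 day 169, dose 8 day 197 and dose 13 day 337.

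**Sunitinib.** After four tremelimumab doses the bar ends on day 85 + 90 = 175. A patient who stops at dose 4 or earlier had the last tremelimumab dose on the day of the last dose, so the overlap is 90 − offset. A patient who stops later has an overlap of 175 − (day of last dose + offset), floored at zero.

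| Last dose received | Offset 0 | Offset 28 | Offset 30 |
|---|---|---|---|
| Dose 4 or earlier | 90 | 90 − 28 = 62 | 90 − 30 = 60 |
| Dose 5 (day 113) | 175 − 113 = 62 | 175 − 141 = 34 | 175 − 143 = 32 |
| Dose 6 (day 141) | 175 − 141 = 34 | 175 − 169 = 6 | 175 − 171 = 4 |
| Dose 7 (day 169) | 175 − 169 = 6 | 0 | 0 |
| Dose 8 (day 197) or later | 0 | 0 | 0 |

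For patients who stop by dose 6 without delays, some overlap remains under all three starts. From dose 8 the bar has expired while the patient is still on durvalumab.

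**Live vaccines.** Overlap = 30 − offset: 30, 2 and 0 days.

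**Effect of a dose hold.** If a patient is removed only after the full 12-week hold, 84 days have passed since the last dose. If that was also the last tremelimumab dose, and follow-up starts at removal, the sunitinib overlap is 90 − 84 = 6 days and the vaccine overlap is zero.

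**The case against.** The strongest reply is that a specific instruction overrides a general one. The sunitinib bullet names the drug, the window and the reason, and it stands close to the closing sentence, so a careful site would follow it. That is a fair account of how most readers would behave. It still leaves a safety bar dependent on the reader choosing the right rule of interpretation, and the lead-in points the other way.

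On vaccines the reply is stronger. Criterion 3.2.22 states the bar independently. The protocol also uses 30 days after the last dose as a boundary elsewhere, for recording concomitant medication (5.3) and for expedited adverse-event reporting (7.4.3). If follow-up starts then, there is no vaccine conflict.

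It is also right that the day counts rest on assumed phase starts and undelayed cycles. They are bounds, not estimates.

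A reader might infer more from this section than it supports:

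- **That the sentence on removing patients who need a listed treatment forces out users of laxatives, physiologic steroids or agreed herbal remedies.** The list is headed as prohibited use, and each of those items is conditionally permitted by its own bullet. Section 5.3 settles continuation case by case between the investigator, CTEP and the patient.
- **That the same sentence conflicts with Section 6 or 3.2.13.** The Section 6 text on low-dose prednisone concerns immune-related endocrinopathies, and the glucocorticoid bullet already largely exempts steroids for suspected immune events. Criterion 3.2.13 is an entry exception.
- **That the laxative and EGFR-inhibitor bullets are contradicted too.** After dosing they ask for caution; they do not bar use.
- **That efficacy data are at risk.** Follow-up and response assessment are required by 5.5 and 13.9.2 whatever this sentence says.

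**Conclusion.** The contradiction is real but small. It is firmest for sunitinib: at most 90 days, confined to patients who stop treatment within about 90 days of their last tremelimumab dose, and shorter when removal follows a hold. It is weaker for live vaccines: 0 to 30 days, with 3.2.22 as a backstop.

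The documents give neither the number of patients who would stop that early nor any sign that sunitinib would be used in these lung and colorectal cohorts, so no count of patients at risk can be given. No endpoint, power or error rate changes. This is a minor patient-safety correction.

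**What to change.** Begin the closing sentence of 5.3 with the clause *Except for the post-dose windows stated above and in 3.2.22,* and leave the rest as it stands. That also settles the lead-in, because the section would then state that those windows extend beyond treatment. Which drugs are restricted, and for how long, remains with the clinical team.

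As an optional editorial note, the removal sentence could say that it covers only use the list does not permit.

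The cost is one clause in one sentence, with no added visits, procedures or patients.

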5.4 Duration of Therapy

In the absence of treatment delays due to adverse event(s), treatment may continue for 12 months or until one of the following criteria applies which would prompt permanent discontinuation of study treatment:

- Disease progression
- Intercurrent illness that prevents further administration of treatment
- Unacceptable adverse event(s), as defined in Section 6.
- Patient decides to withdraw from the study
- General or specific changes in the patient's condition render the patient unacceptable for further treatment in the judgment of the investigator
- Patient non-compliance
- Pregnancy
 - All women of child bearing potential should be instructed to contact the investigator immediately if they suspect they might be pregnant (e.g., missed or late menstrual period) at any time during study participation.
 - The investigator must immediately notify CTEP in the event of a confirmed pregnancy in a patient participating in the study.
- Termination of the study by sponsor
- The drug manufacturer can no longer provide the study agent

The reason(s) for protocol therapy discontinuation, the reason(s) for study removal, and the corresponding dates must be documented in the Case Report Form (CRF).

5.5 Duration of Follow Up

Patients will be followed for at least 12 weeks after removal from study treatment or until death, whichever occurs first. Patients removed from study treatment for unacceptable adverse event(s) will be followed until progression. All patients will be followed for at least a year from the time of initiation of treatment.

5.6 Criteria for Removal from Study

When study treatment is terminated per the criteria in Section 5.4 patients will remain on study follow-up. Study follow-up will be terminated at death or for at least one year from the time of treatment initiation and at least 12 weeks after removal from study treatment, whichever occurs first. Patients removed from study treatment for unacceptable adverse event(s) will continue on study follow-up until the preceding criteria are met or disease progression, whichever occurs later. The reason for study removal and the date the patient was removed must be documented in the Case Report Form.

5.7 Criteria to Resume Treatment

For non-autoimmune or inflammatory events, patients may resume treatment with study drug according to section 6.

If the criteria to resume treatment are met, the patient should restart treatment no sooner than the next scheduled time point per protocol. However, if the treatment is delayed past the next scheduled time point per protocol, the treatment should resume at the earliest convenient point that is within the 12 week delay period.

If treatment is delayed >12 weeks, the patient must be permanently discontinued from study therapy, except as specified in Section 5.4 (Duration of Therapy).

5.8 Treatment Beyond Progression

Immunotherapeutic agents such as MEDI4736 and tremelimumab may produce antitumor effects by potentiating endogenous cancer-specific immune responses. The response patterns seen with such an approach may extend beyond the typical time course of responses seen with cytotoxic agents, and can manifest as a clinical response after an initial increase in tumor burden or even the appearance of new lesions.

If radiologic imaging shows progressive disease (PD), tumor assessment may be repeated by the site approximately 4-8 weeks later in order to confirm continued PD (as compared to the initial scan) with the option of continuing treatment per below while awaiting radiologic confirmation of progression, provided there are less than 5 new lesions, and the total tumor burden demonstrates less than 40% increased growth as compared to the initial scan. Additionally, any new CNS lesions must be treated prior to resuming therapy. If repeat imaging shows a reduction or stabilization in the tumor burden compared to the initial scan demonstrating PD, treatment may be continued as per treatment calendar. If repeat imaging confirms continued PD, patients will be discontinued from study therapy. If reimaging is no worse than the prior scan 4 weeks prior, patients may continue therapy and be reimaged in another 8 weeks. If evidence for continued, increasing progression with subsequent imaging, the patient will be discontinued. In determining whether or not the tumor burden has increased or decreased, investigators should consider all target lesions as well as non-target lesions. The decision to continue study treatment after the first evidence of disease progression determined by radiologic imaging is at the Investigator's discretion based on the clinical status of the patient as described in the table below.

	Clinically Stable		Clinically Unstable	
	Imaging	Treatment	Imaging	Treatment
1 st radiologic evidence of PD	Repeat imaging at approximately 4 weeks to confirm PD	May continue study treatment at the Investigator's discretion while awaiting confirmatory scan	Repeat imaging at approximately 4 weeks to confirm PD if possible	Discontinue treatment
Repeat scan confirms PD	No additional imaging required	Discontinue treatment	No additional imaging required	N/A
Repeat scan shows SD, PR, or CR	Continue regularly scheduled imaging assessments every 6 weeks	Continue study treatment at the Investigator's discretion	Continue regularly scheduled imaging assessments every 6 weeks	May restart study treatment if condition has improved and/or clinically stable per Investigator's discretion
Tumor imaging will be assessed every 12 weeks (84 ±7 days).				

Patients may receive study treatment while waiting for confirmation of continued PD if they are clinically stable as defined by the following criteria:

- Absence of signs and symptoms (including worsening of laboratory values) indicating disease progression^{[[SEP]]}
- No decline in ECOG performance status^{[[SEP]]}
- Absence of rapid progression of disease
- Absence of progressive tumor at critical anatomical sites (e.g., cord compression) requiring urgent alternative medical intervention
- No urgent need for radiation therapy other than as specified by the protocol

5.9 Discontinuation of Treatment Following Complete Response

Discontinuation of treatment may be considered for patients who have attained a confirmed complete response (CR) that have been treated for at least 52 weeks on protocol and had at least two treatments with MEDI4736 beyond the date when the initial CR was declared.

NCI Protocol #: 10021
Version Date: 08/30/2019

6. DOSING DELAYS/DOSE MODIFICATIONS- Dosing Modification And Toxicity Management Guidelines For Immune-Mediated, Infusion Related, And Non-Immune-Mediated Reactions (Medi4736 Monotherapy Or Combination Therapy With Tremelimumab Or Tremelimumab Monotherapy) 1 November 2017 Version

General Considerations	
Immune-related Adverse Events (Overall Management For toxicities not noted below)	Toxicity Management

Dose Modifications
 
Drug administration modifications of study drug/study regimen will be made to manage potential immune-related AEs based on severity of treatment-emergent toxicities graded per NCI CTCAE v5.0. In addition to the criteria for permanent discontinuation of study drug/regimen based on CTC grade/severity (table below), permanently discontinue study drug/study regimen for the following conditions:
 
 • Inability to reduce corticosteroid to a dose of ≤ 10 mg of prednisone per day (or equivalent) within 12 weeks after last dose of study drug/study regimen • Recurrence of a previously experienced Grade 3 treatment-related AE following resumption of dosing. 
Grade 1 No dose modification
 
Grade 2 Hold study drug/study regimen dose until grade 2 resolution to \leq Grade 1**
 
 • If toxicity worsens then treat as Grade 3 or Grade 4 • Study drug/study treatment can be resumed once event stabilizes to grade ≤ 1 after completion of steroid taper 
Patients with endocrinopathies who may require prolonged or continued steroid replacement can be retreated with study drug/study regimen on the following conditions: 1) the event stabilizes and is controlled, 2) the patient is clinically stable as per Investigator or treating physician's clinical judgement, and 3) doses of prednisone are at less than or equal to 10mg/day or equivalent.
 
Grade 3 Depending on the individual toxicity, study drug/study regimen may be permanently discontinued. Please refer to guidelines below
	
It is recommended that management of immune-mediated adverse events (imAEs) follows the guidelines presented in this table
 
 - It is possible that events with an inflammatory or immune mediated mechanism could occur in nearly all organs, some of them not noted specifically in these guidelines. - Whether specific immune-mediated events (and/or laboratory indicators of such events) are noted in these guidelines or not, patients should be thoroughly evaluated to rule out any alternative etiology (e.g., disease progression, concomitant medications, and infections.) to a possible immune-mediated event. In the absence of a clear alternative etiology, all such events should be managed as if they were immune related. General recommendations follow. 
 - Symptomatic and topical therapy should be considered for low-grade (Grade 1 or 2, unless otherwise specified) events - For persistent (greater than 3 to 5 days) low-grade (Grade 2) or severe (Grade ≥ 3) events promptly start prednisone PO 1-2mg/kg/day or IV equivalent - Some events with high likelihood for morbidity and/or mortality – e.g., myo-carditis, or other similar events even if they are not currently noted in the guidelines – should progress rapidly to high dose IV corticosteroids (methylprednisolone at 2 to 4 mg/kg/day) even if the event is Grade 2, and if clinical suspicion is high and/or there has been clinical confirmation. Consider, as necessary, discussing with the study physician, and promptly pursue specialist consultation. - If symptoms recur or worsen during corticosteroid tapering 28 days of taper), increase the corticosteroid dose (prednisone dose [e.g. up to 2-4mg/kg/day PO or IV equivalent]) until stabilization or improvement of symptoms, then resume corticosteroid tapering at a slower rate (≥ 28 days of taper) - More potent immunosuppressives such as TNF inhibitors (e.g. infliximab) – (also refer to the individual sections of the immune related adverse event for specific type of immunosuppressive) should be considered for events not responding to systemic steroids. Progression to use of more potent immunosuppressives should proceed more

	
Grade 4 Permanently discontinue study drug/study regimen
 
Note: For Grade ≥ 3 asymptomatic amylase or lipase levels, hold study drug/study regimen, and if complete work up shows no evidence of pancreatitis, study drug/study regimen may be continued or resumed.
 
Note: Study drug/study regimen should be permanently discontinued in Grade 3 events with high likelihood for morbidity and/or mortality – e.g., myocarditis, or other similar events even if they are not currently noted in the guidelines. Similarly, consider whether study drug/study regimen should be permanently discontinued in Grade 2 events with high likelihood for morbidity and/or mortality – e.g., myocarditis, or other similar events if they are not currently noted in the guidelines – when they do not rapidly improve to Grade < 1 upon treatment with systemic steroids and following full taper
 
Note: There are some exceptions to permanent discontinuation of study drug for Grade 4 events (i.e., hyperthyroidism, hypothyroidism, Type 1 diabetes mellitus).
 
** Note: If AE's develop in an interval where the next scheduled treatment is radiation (either low or high dose), radiation may be continued at the treating physician's discretion if the radiation treatment field is clearly unrelated to the AE (e.g. liver radiation in a patient who develops pneumonitis), provided the patient is clinically stable and willing to proceed with radiation treatment.
	
rapidly in events with high likelihood for morbidity and/or mortality – e.g., myocarditis, or other similar events even if they are not currently noted in the guidelines – when these events are not responding to systemic steroids.
 
 - With long-term steroid and other immunosuppressive use, consider need for Pneumocystis jirovecii pneumonia (PJP, formerly known as Pneumocystis carinii pneumonia) prophylaxis, gastrointestinal protection, and glucose monitoring. - Discontinuation of study drug is not mandated for Grade 3 / Grade 4 inflammatory reactions attributed to local tumour response (e.g. inflammatory reaction at sites of metastatic disease, lymph nodes etc.). Continuation of study drug in this situation should be based upon a benefit/risk analysis for that patient
--	--	--

Specific Immune -Mediated Reactions

	Grade of the Event (NCI CTCAE version 4.03)	Dose Modifications	Toxicity Management
Pneumonitis/ Interstitial Lung Disease (ILD)	Any Grade	General Guidance	
For Any Grade
 
 - Monitor patients for signs and symptoms of pneumonitis or ILD (new onset or worsening shortness of breath or cough). Patients should be evaluated with imaging and pulmonary function tests including other diagnostic procedures as described below - Initial work-up may include clinical evaluation, monitoring of oxygenation via pulse oximetry (resting and exertion), laboratory work-up and high-resolution CT scan.
	Grade 1 (Asymptomatic, clinical or diagnostic observations only, intervention not indicated)	No dose modification required. However, consider holding study drug/study regimen dosing as clinically appropriate and during diagnostic work-up for other etiologies	
For Grade 1 (Radiographic Changes Only)
 
 - Monitor and closely follow up in 2-4 days for clinical symptoms, pulse oximetry (resting and exertion) and laboratory work-up and then as clinically indicated - Consider Pulmonary and Infectious disease consult
	Grade 2 (Symptomatic, medical intervention indicated, limiting instrumental ADL)	Hold study drug/study regimen dose until grade 2 resolution to ≤ Grade 1 
 • If toxicity worsens then treat as Grade 3 or Grade 4 • If toxicity improves to Grade ≤1, then the decision to reinstitute study drug/regimen at next scheduled treatment date will be 	
For Grade 2 (Mild to Moderate New Symptoms)
 
 - Monitor symptoms daily and consider hospitalization - Promptly start systemic steroids (e.g., prednisone 1-2mg/kg/day PO or IV equivalent) - Reimaging as clinically indicated - If no improvement within 3-5 days, additional workup should be considered and prompt treatment with IV methylprednisolone 2-4mg/kg/day started - If still no improvement within 3-5 days despite IV

	Grade of the Event (NCI CTCAE version 4.03)	Dose Modifications	Toxicity Management
		based upon treating physician's clinical judgment and after completion of steroid taper	
methylprednisolone at 2-4/g/kg/day, promptly start immunosuppressive therapy such as TNF inhibitors (e.g. infliximab at 5mg/kg every 2 weeks). Caution: It is important to rule out sepsis and refer to infliximab label for general guidance before using infliximab
 
 - Once the patient is improving, gradually taper steroids over ≥28 days and consider prophylactic antibiotics, antifungal or anti PCP treatment (refer to current NCCN guidelines for treatment of cancer-related infections (Category 2B recommendation)^{1,23} - Consider pulmonary and infectious disease consult - Consider as necessary discussing with study physician

Grade 3 or 4 (Grade 3: Severe symptoms; limiting self-care ADL; oxygen indicated; Grade 4: life threatening respiratory compromise, urgent intervention indicated [e.g. tracheostomy or intubation])
	Permanently discontinue study drug/study regimen	
For Grade 3 or 4 (severe or new symptoms, new/worsening hypoxia, life threatening
 
 - Promptly initiate empiric IV methylprednisolone 1 to 4 mg/kg/day or equivalent - Obtain Pulmonary and Infectious disease consult; consider, as necessary, discussing with study physician. - Hospitalize the patient - Supportive Care (oxygen, etc.) - If no improvement within 3-5 days, additional workup should be considered and prompt treatment with additional immunosuppressive therapy such as TNF inhibitors (e.g. infliximab at 5mg/kg every 2 weeks dose) started. Caution: rule out sepsis and refer to infliximab label for general guidance before using infliximab - Once the patient is improving, gradually taper steroids over ≥28 days and consider prophylactic antibiotics, antifungals and in particular, anti PJP treatment (please refer to current NCCN 	

¹ ASCO Educational Book 2015 “Managing Immune Checkpoint Blocking Antibody Side Effects” by Michael Postow MD

² NCI CTCAE version 4.03

³ ASCO Educational Book 2015. Michael Postow MD. “Managing Immune Checkpoint Blocking Antibody Side Effects”

	Grade of the Event (NCI CTCAE version 4.03)	Dose Modifications	Toxicity Management
			guidelines for treatment of cancer-related infections (Category 2B recommendation) ⁴
Diarrhea/ Colitis	Grade of Diarrhea (CTCAE version 4.03)	Any Grade	
 - Monitor for symptoms that may be related to diarrhea/enterocolitis (abdominal pain, cramping, or changes in bowel habits such as increased frequency over baseline or blood in stool) or related to bowel perforation (such as sepsis, peritoneal signs and ileus) - Patients should be thoroughly evaluated to rule out any alternative etiology (e.g., disease progression, other medications, infections including testing for clostridium difficile toxin, etc.) - Steroids should be considered in the absence of clear alternative etiology, even for low grade events, in order to prevent potential progression to higher grade event - Use analgesics carefully; they can mask symptoms of perforation and peritonitis
Grade 1 (Diarrhea:stool frequency of <4 over baseline per	Grade 1 (Diarrhea:stool frequency of <4 over baseline per	No dose modification	
For Grade 1 diarrhea :
 
 - Close monitoring for worsening symptoms - Consider symptomatic treatment including hydration, electrolyte

⁴ ASCO Educational Book 2015 “Managing Immune Checkpoint Blocking Antibody Side Effects” by Michael Postow MD

	Grade of the Event (NCI CTCAE version 4.03)	Dose Modifications	Toxicity Management
	
day) (Colitis: asymptomatic; clinical or diagnostic observations only)
 
Grade 2 (Diarrhea: stool frequency of 4-6 over baseline per day) (Colitis: abdominal pain; mucus or blood in stool)
	
Hold study drug/study regimen until resolution to ≤ Grade 1
 
 • If toxicity worsens then treat as Grade 3 or Grade 4 • If toxicity improves to Grade ≤1, then study drug/study regimen can be resumed after completion of steroid taper 	
replacement, dietary changes (e.g., American Dietetic Association colitis diet), and loperamide. Use of probiotics as per treating physician's clinical judgment.
 
For Grade 2 diarrhea:
 
 - Consider symptomatic treatment including hydration, electrolyte replacement, dietary changes (e.g., American Dietetic Association colitis diet), and loperamide and/or budesonide - Promptly start prednisone 1 to 2 mg/kg/day PO or IV equivalent - If event is not responsive within 3-5 days or worsens despite prednisone at 1-2 mg/kg/day PO or IV equivalent, GI consult should be obtained for consideration of further workup such as imaging and/or colonoscopy to confirm colitis and rule out perforation, and prompt treatment with IV methylprednisolone 2-4mg/kg/day started. - If still no improvement within 3-5 days despite 2-4mg/kg IV methylprednisolone, promptly start immunosuppressives such as (infliximab at 5mg/kg once every 2 weeks⁵). . Caution: It is important to rule out bowel perforation and refer to infliximab label for general guidance before using infliximab - Consider, as necessary, discussing with study physician if no resolution to ≤ Grade 1 in 3-4 days - Once the patient is improving, gradually taper steroids over ≥28 days and consider prophylactic antibiotics, antifungals and anti PJP treatment (please refer to current NCCN guidelines for treatment of cancer-related infections [Category 2B recommendation])

	Grade of the Event (NCI CTCAE version 4.03)	Dose Modifications	Toxicity Management
	
Grade 3 or 4 diarrhea
 
(Grade 3 diarrhea: stool frequency of ≥ 7 over baseline per day;
 
Grade 4 diarrhea: life threatening consequences)
 
(Grade 3 colitis: severe abdominal pain, change in bowel habits, medi-cal intervention indicated, peritoneal signs;
 
Grade 4 colitis: life-threatening consequences, urgent intervention indicated)
	
Grade 3
 
Permanently discontinue study drug/study regimen for Grade 3 if toxicity does not improve to Grade ≤ 1 within 14 days; study drug/study regimen can be resumed after completion of steroid taper.
 
Grade 4
 
Permanently discontinue study drug/study regimen.
	
For Grade 3 or 4 diarrhea:
 
 - Promptly initiate empiric IV methylprednisolone 2 to 4 mg/kg/day or equivalent - Monitor stool frequency and volume and maintain hydration - Urgent GI consult and imaging and/or colonoscopy as appropriate - If still no improvement within 3-5 days of IV methylprednisolone 2 to 4mg/kg/day or equivalent, promptly start further immunosuppressives (e.g. infliximab at 5mg/kg once every 2 weeks). - Caution: Ensure GI consult to rule out bowel perforation and refer to infliximab label for general guidance before using infliximab. - Once the patient is improving, gradually taper steroids over ≥ 28 days and consider prophylactic antibiotics, antifungals and anti PJP treatment (please refer to current NCCN guidelines for treatment of cancer-related infections [Category 2B recommendation])

Hepatitis (Elevated LFTs) Infliximab should not be used for
	
Grade of Liver Function Test Elevation (CTCAE version 5.0) Any Grade
		
 - Monitor and evaluate liver function test: AST, ALT, ALP and total bilirubin - Evaluate for alternative etiologies (e.g., viral hepatitis, disease progression, concomitant medications)

	Grade of the Event (NCI CTCAE version 4.03)	Dose Modifications	Toxicity Management

management of Immune Related Hepatitis
	
Grade 1 (Based on ULN regardless of baseline LFT) (AST or ALT >ULN and $\leq 3.0 \times$ULN and/or TB > ULN and $\leq 1.5 \times$ULN)
	
No dose modifications If it worsens, then treat as Grade 2 event
	
For Grade 1 AST or ALT and/or TB elevation
 
 - Continue LFT monitoring per protocol
